1. PERSONAL INFORMATION

1.1 Title [name] [name] Other
 1.3 Last Name _____
 1.5 Date of Birth [DD/MM/YY] _____
 1.7 Area of Residence _____
 1.9 Occupation _____
 1.11 ID Type National ID Passport Driver's License Voter ID NHIS Card Student ID Employment ID
 1.12 Phone Number 1.13 E-mail _____
 1.14 Preferred Contact Method Phone SMS E-mail Do not contact for blood donation

2. DONATION HISTORY

2.1 Have you donated blood before? Yes No 2.2 If Yes, last donation date? [DD/MM/YY] _____
 2.3 How many times as Voluntary _____ Replacement _____ 2.4 Donor Card # _____

3. REPLACEMENT/FAMILY DONORS ONLY

3.1 Name of Patient _____ 3.2 Hospital _____
 3.3 Ward _____ 3.4 Relationship to Patient _____
 Name of Clerking Officer _____ Signature of Clerking Officer _____

Please turn over to proceed to Section 4 →

OFFICE USE ONLY

5. DONOR SELECTION

5.1 Appearance Passed Failed 5.2 Medical History Passed Failed 5.3 Weight _____ kg
 5.4 Blood Pressure _____ mmHg 5.5 Pulse _____ bpm 5.6 Hb by CuSO₄ Passed Failed
 5.7 Hb checked _____ g/dL 5.8 HBsAg checked? Yes No HBsAg Result _____

5.9 Outcome of Screening:

| Qualifies to Donate | Permanently Deferred | Temporarily Deferred | Duration of Temporary Deferral |
|------------------------------|--|--|--------------------------------------|
|  Yes |  High Risk Behaviour |  Low Hb |  1 week |
|  No |  Medical Condition |  Low Weight |  1 month |
| |  Test Outcome |  Medical Condition |  6 months |
| Comments: _____ | |  Iron Stores Risk |  ≥1 year |
| | |  TTI Risk |  Other _____ |
| | |  Other _____ | |
| | | Name of Nurse _____ | Signature _____ |

6. BLOOD DONATION

6.1 Donation Number: _____ 6.2 Pack Type Single Double Triple Quad
 6.3 Bleed Time: Start _____ End _____ Dry Pack Apheresis Test Only Did not bleed
 6.4 Outcome of Phlebotomy Successful Unsuccessful please specify: Venous Access Underbled _____ mL Donor Reaction
 6.5 Donor Adverse Event: Vasovagal Reaction (mild) Vasovagal Reaction (complicated or with injury)
 Haematoma/Abnormal Bleed Painful Arm Multiple Pricks Other _____

Name of Nurse _____

Signature _____

4. HEALTH QUESTIONNAIRE

Blood donation should be safe for both the donor and the eventual recipient of the blood donated. The following questions will help us determine whether it is safe for YOU to donate blood today, and whether the blood is likely to be safe enough to give to a sick person. We cannot rely entirely on laboratory tests, as they may not always be able to detect infectious agents and other problems, so please answer the questions TRUTHFULLY. Thank you!

Please check “✓” in the boxes and qualify responses by underlining the specific item that applies.

| | |
|--|--|
| 1. Are you feeling well today, i.e. no fever, cough, headache or cold? | Yes  No  |
| 2. Have you ever been deferred as a blood donor or told not to donate blood? If Yes, for what reason? _____ | Yes  No  |
| 3. Are you taking medication? If Yes, for what condition? _____ and what medication? _____ | Yes  No  |
| 4. Have you had, or do you have epilepsy, stomach ulcer, heart disease or cancer? | Yes  No  |
| 5. Have you had tuberculosis? | Yes  No  |
| 6. Have you been vaccinated in the last 4 weeks? If Yes, what vaccine? _____ | Yes  No  |
| 7. Have you had jaundice, liver disease or a positive blood test for hepatitis? | Yes  No  |
| 8. Do you have sickle cell disease (not sickle trait, 'AS'), or joint pains that usually occur during cold seasons? | Yes  No  |
| 9. Have you ever injected yourself with drugs or medication? | Yes  No  |
| 10. Have you in the last 6 months had a needle-stick injury or an injection in a place that is not a hospital or clinic; or skin scarring/tattoo; or cutting by a traditional healer (including circumcision)? | Yes  No  |
| 11. Have you ever had a headache? | Yes  No  |
| 12. Have you had dental treatment in the last 1 week, or taking antibiotics now? | Yes  No  |
| 13. Have you in the past 6 months had any surgery with general anaesthesia? | Yes  No  |
| 14. Have you in the last 6 months received blood or blood component transfusion? | Yes  No  |
| 15. Have you in the last 6 months lost more than 5kg in weight unintentionally? | Yes  No  |
| 16. Have you in the last 6 months had unprotected sex with more than one partner or have paid/been paid to have sex? | Yes  No  |
| 17. Have you ever had gonorrhoea, genital or urinary pain or discharge? | Yes  No  |
| 18. [For Men Only] Have you in the last 6 months had sex with a man? | Yes  No  |
| 19. Have you or your partner ever tested positive for HIV (AIDS)? | Yes  No  |
| 20. After blood donation, are you going to take part in any vigorous activity, such as climbing, driving a heavy vehicle, operating heavy machinery, or working at hazardous areas or heights? | Yes  No  |
| 21. Are you coming to donate blood because you have been told you have too much blood? | Yes  No  |
| 22. Have you been pregnant in the last 12 months or currently breastfeeding? | Yes  No  |
| Additional question(s) _____ | |

[figure not shown]
Refer to the “*Medical History Selection Guide for Donor Attendants*” in the Donor Selection & Care Manual to guide your evaluation of the donor.

APPENDIX 4: Study Design Flowchart

APPENDIX 5: Study Timelines**BLOOSAFE Ghana Site Project - UG3 Timelines**

| UG 3 | ACTIVITY | YEAR 1 | | | | | | YEAR 2 | | | | | | | | | | | | | | |
|----------|---|-------------|-------------|-------------|-------------|-------------|-------------|-------------|-------------|-------------|-------------|-------------|-------------|-------------|-------------|-------------|-------------|-------------|-------------|-------------|-------------|-------------|
| | | 2020 | | | 2021 | | | 2022 | | | | | | | | | | | | | | |
| | | J U L | A U G | S E P | C O T | N B R | D E Y | M A R | A P R | M A Y | J U N | J U L | A U G | S E P | O C O | N B R | D E Y | J U N | F A B | M A R | A P R | M A Y |
| 1 | Systematic Literature Review | | | | | | | | | | | | | | | | | | | | | |
| | Protocol Development | | | | | | | | | | | | | | | | | | | | | |
| | Literature Search | | | | | | | | | | | | | | | | | | | | | |
| | Data Extraction | | | | | | | | | | | | | | | | | | | | | |
| | Data Analysis & Synthesis | | | | | | | | | | | | | | | | | | | | | |
| | Write up | | | | | | | | | | | | | | | | | | | | | |
| | Revisions and submission | | | | | | | | | | | | | | | | | | | | | |
| 2 | Study Protocol Development and Approvals | | | | | | | | | | | | | | | | | | | | | |
| | Protocol Version 0.1 | | | | | | | | | | | | | | | | | | | | | |
| | Steering C'tee Review 1 | | | | | | | | | | | | | | | | | | | | | |
| | Protocol Version 0.2 | | | | | | | | | | | | | | | | | | | | | |
| | Steering C'tee Review 2 | | | | | | | | | | | | | | | | | | | | | |
| | Protocol Version 0.3 | | | | | | | | | | | | | | | | | | | | | |

## 1 Introduction

### 1.1 Objective of the statistical analysis plan

The objective of this statistical analysis plan (SAP) is to describe how quantitative interim and final data from the pilot study entitled “Iron Supplementation and Nutritional Counseling Interventions to Improve Availability and Safety of Blood in Ghana” will be analysed. The short name is “Bloodsafe Ghana- Iron and Nutritional Counseling Strategy Pilot Study” with acronym BLIS. This version of the SAP was based on version 1.0 of the protocol and may be modified prior to modifications of version 1.0 of the protocol. Alternatively, newer versions of the study protocol may still use this version of the SAP.

This SAP:

- Provides a brief background of the study (section 1.2).
- Provides details on statistical aspects of the study design (sections 2.1-2.4).
- Describes goals of the interim review by the independent data and safety monitoring board (DSMB), the planned format of the review meetings, and timing of final analyses (sections 2.6-2.7).
- Describes the trial population used for analysis (section 3).
- Describes the planned data analyses that will be included in reports to the DSMB (sections 4-7).
- Describes data summaries to be provided regularly to the DSMB and study leadership to aid in monitoring trial conduct and data quality; these data summaries will be restricted to enrolment, baseline data, data completeness, and study conduct, and will be pooled across treatment groups (See section 8).

The SAP for BLIS may be updated after enrolment begins but will be finalized prior to database lock. These updates will be distinguished by new version numbers (with updated dates). A table after the title page of this document will summarize any changes.

### 1.2 Description of the study

This section briefly summarizes the rationale and approach of BLIS. The study protocol provides greater detail. Details on statistical topics (e.g., sample size and analysis) beyond what the study protocol provides will be described in later sections of this SAP.

#### Rationale

The major challenge for blood transfusion services in Sub-Saharan Africa is the juxtaposition of an increasing clinical demand for blood and a historically insufficient supply of safe blood in the region. The system of blood donation in Ghana has been identified as the major barrier to providing adequate and regular blood to meet the transfusion needs of the country. This study is therefore planned as a feasibility and acceptability pilot trial of iron supplementation to increase blood donation among blood donors deferred for low levels of haemoglobin within the catchment areas of the Southern Zonal Blood Centre (SZBC).

## Design

This pilot study has 3 components: 1) a cross-sectional assessment designed to estimate the prevalence of anaemia leading to donor deferral, 2) a cross-sectional assessment designed to estimate the prevalence of iron deficiency (ID) and the prevalence of iron deficiency anaemia (IDA) among first-time donors, and 3) a longitudinal 2-arm parallel groups trial among first-time voluntary donors that compares haemoglobin levels at 4 months among those who receive iron supplementation at enrolment to those who do not receive iron supplementation at enrolment.

The primary outcome for the trial will be haemoglobin levels at 4 months. Participants will be followed for a total of 6 months with study visits at 2, 4 and 6 months after the baseline assessment. Blood draws for a full blood count (FBC), peripheral film comment, malaria rapid test and ferritin assessment and the administration of a structured questionnaire will occur at screening, 2 months (interim 1), 4 months (interim 2) and final visits (6 months). The malaria rapid test occurs at the enrolment visit which occurs within 3 weeks of the screening visit. There is not a blood draw at the enrolment visit unless the participant presents with signs of infection.

The parallel group's component is designed as a non-inferiority trial for haemoglobin levels at 4 months. At baseline, the 2 groups will be determined based on the need for iron supplementation: all individuals with ID, IDA or low haemoglobin (gender specific values), who satisfy our eligibility criteria regardless of deferral status, will receive iron supplements while all others will not. While a high prevalence of ID and IDA is expected, enrolment will be staggered so that an equal number of participants from each group are enrolled from each site with at least 1 participant who is assigned to iron supplementation. If there are more potential participants in one group at some site, randomization will be used to select the individuals to enroll in the trial to maintain balance over time. The extent of adherence is a central question for this study, and it is also unclear if the haemoglobin deficiency can be improved above what is seen in the control group, hence it is not hypothesized that those receiving iron supplementation will have higher levels of haemoglobin at 4 months. The hypothesis about the iron supplementation intervention is that it will improve haemoglobin levels to near that seen among those who did not receive iron supplementation. If haemoglobin levels are higher in those receiving iron supplementation the intervention would also be deemed a success. Hence a non-inferiority trial is most appropriate for this hypothesis.

Selection of the margin is a critical component of a non-inferiority trial. Here, we specify a margin of 1 g/dL for haemoglobin levels at 4 months. Under a collection of reasonable assumptions, this margin will ensure that the majority of those with low haemoglobin at screening will have haemoglobin levels at 4 months above the threshold for anaemia and should therefore qualify as donors. To see this, assume that half of donors are anaemic at screening (using the thresholds for anaemia of 13 g/dL for men and 11.5 g/dL for women). A simple calculation finds that if we assume haemoglobin levels are normally distributed (which is a reasonable assumption based on observed distributions for haemoglobin in unselected individuals in West Africa) and the standard deviation of screening haemoglobin levels is 1.89 g/dL (this estimate will be described below) then the mean haemoglobin level among men who are deferred is 11.5 g/dL and the mean haemoglobin level among men who are not deferred is 14.5 g/dL (these values for

women are 10.0 g/dL and 13.0 g/dL). If we assume that the haemoglobin level among those who are not deferred is the same 4 months later then a margin of 1 g/dL implies a mean haemoglobin level among those with anaemia at screening of at least 13.5 g/dL for men and 12.0 g/dL for women. Thus, the mean haemoglobin level after 4 months of iron supplementation among those who should have been deferred will exceed the threshold for anaemia and consequently, if the distribution of haemoglobin levels is symmetric, the majority of those who were anaemic at screening would qualify as donors (in fact at least 60.4% would pass the threshold for both sexes if this distribution is normal). Note that the threshold for the copper sulphate test used for women is 12 g/dL, not 11.5 g/dL, so under these assumptions 50% of women would pass the copper sulphate test. Nonetheless, since well over 50% of donors are men the majority of deferred donors would pass the copper sulphate test. It is likely that fewer than half of all donors will be anaemic at screening. In this case the difference in the means between those with anaemia and those without anaemia will be larger, the gain in haemoglobin levels in the anaemic group will be larger and the proportion of donors who would be deferred at screening but would not be deferred after 4 months of iron supplementation will be even larger. It is possible that the difference between the 2 groups is smaller than the margin at screening. This seems unlikely since the 2 groups are defined by a threshold for haemoglobin levels, but if the standard deviation of haemoglobin levels is 0.62 then the difference between the groups among men would be less than the margin under the assumptions of the previous paragraph (this standard deviation is less than one third of the standard deviation used for design). To address this, when enrolment reaches 50% of the total planned sample size, the statisticians supporting the trial at the data coordinating centre (DCC) will compute the standard deviation of haemoglobin levels at screening and revisit the margin calculation and the sample size. If the standard deviation is low enough so that the difference between the groups is less than the margin, then the study will be overpowered for the current margin and a smaller margin will be selected so that the trial is still testing for differences at 4 months that exceed the screening difference. Any changes to the study design based on these analyses will be discussed with the DSMB.

In addition, we will use a qualitative approach to identify barriers and facilitators of blood donation and the use of dietary and iron supplementation strategies to address ID and/or anaemia. This will involve conducting focus group discussions (FGDs) during the last month of the intervention. The interviews will focus on multiple issues including food selection and consumption, cost of micronutrient-rich foods as well as other potential issues that might contribute to the success or otherwise of the dietary and iron supplementation interventions.

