**Table 2: Precision of prevalence estimates for ID and IDA.**

Prevalence	Error Margin	95% Confidence Interval
0.2	0.046	0.15, 0.25
0.3	0.053	0.25, 0.35
0.4	0.056	0.34, 0.46
0.5	0.057	0.44, 0.56

**Parallel groups study:** The primary outcome for this portion of the study is haemoglobin levels at 4 months. Formally the null hypothesis for this outcome is inferiority of treatment of low haemoglobin with iron supplementation among those with

low haemoglobin at screening to no treatment among those without low haemoglobin at screening. The non-inferiority margin is fixed at a value of 1.0 g/dL. Based on recent work in West Africa, the DCC has access to haemoglobin measurements from 1548 individuals between the ages of 17 and 60 who weigh at least 50 kg. Among these individuals the standard deviation of haemoglobin was 1.89 g/dL (the mean was 13.4 g/dL). These individuals did not pass the strict screening criteria used by the NBSG, so this estimate might be slightly inflated and so our power calculations may be somewhat conservative. We specify an alpha level of 0.025 and require power of at least 85%. With these values we can determine the number of participants per arm if we assume a value for the true difference between the groups (the absolute value of this difference must be less than our margin and will generally be negative when the margin is positive to be consistent with the lack of superiority of iron supplementation). Table 3 presents the number of participants per arm under these assumptions for a selection of values for the true difference. We assume that the true difference is -0.3 g/dL and obtain a sample size of 131 participants per arm. If the true difference is larger than -0.3 g/dL (e.g., if there is no difference) then the power will exceed 85%. To allow for loss to follow-up and some participants requiring iron supplementation due to incident anaemia, ID or IDA the sample size has been increased to 292.

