### 7.2.1 Primary outcome

The **primary outcome** of the trial is haemoglobin level (g/dl) after 4 months.

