#### Primary analysis

The analysis for the primary outcome of haemoglobin levels at 4 months will be conducted using a linear model with haemoglobin levels at 4 months as the response variable. It is unlikely that there is a need to transform the response variable as haemoglobin levels are usually symmetrically distributed with tails that decay at rates consistent with the normal distribution. However, if informal univariate assessments of normality (e.g., qq-plots) indicate strong departures from these expectations, the Box-Cox transformation will be used to select a transformation. The set of explanatory variables will be group membership (i.e., received iron supplementation at enrolment or not), screening haemoglobin, sex, and age. A 1-sided t-test for the regression coefficient associated with group membership will be conducted with a significance level of 0.025 to test the inferiority hypothesis. This analysis will exclude individuals who did not receive iron supplementation at enrolment but received it during follow-up due to changes in ferritin or haemoglobin values. The frequency of this will be closely tracked and if more than 10% of participants in the group initially not receiving iron supplementation receive iron supplementation during follow-up, alternative analysis approaches will be considered and presented to the DSMB.

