## 7.2.2 Secondary outcomes

### Secondary outcomes related to efficacy

Several secondary outcomes relate to the efficacy of iron supplementation. The treatment of those not requiring iron supplementation at enrolment but requiring iron supplementation during follow-up will be the same as for the primary outcome. These secondary outcomes include:

- Change in haemoglobin over 4 months (g/dl).
- Ferritin levels at 4 months (µg/L).
- Diagnosis of ID or IDA at 4 months (Yes or No).
- Attempt to return for donation within 6 months (Yes or No).
- Successful donation within 6 months (Yes or No).

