## Appendix A. Schedule of Assessments

Assessment	Screening (Day -14 to 0)	Enrolment (Day 0)	Biweekly (Throughout)	Interim Visit 1 (Week 8-10)	Interim Visit 2 (Week 16-18)	Final Visit (Week 24)
NBSG Pre-Donation Assessment	X					X
Informed Consent	X					
Inclusion and Exclusion Criteria	X					
Demographics	X					
Full Blood Count and peripheral blood comment	X			X	X	X
Plasma Ferritin	X			X	X	X
Malaria Parasites Testing (RDT)	X	X		X	X	X
Nutritional Counselling		X		X	X	
Qualitative Assessment						X
Follow-Up Calls			X			
Return Blood Donation Status				X	X	X
Assessment for Adverse Events		X	X	X	X	X
Adherence Assessment (for those receiving supplemental iron)			X	X	X	X
RDT – Rapid Diagnostic Test						

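### The plan infers from a 1 g/dL margin on means that most low-haemoglobin donors will pass the anaemia threshold at 4 months; the primary test cannot show this and no listed efficacy outcome estimates it

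*SAP*

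**What the plan says.** SAP 1.2 (Design), like the Protocol's Design section, justifies the margin by a proportion. After a reference to a set of reasonable assumptions, it states that "this margin will ensure that the majority of those with low haemoglobin at screening will have haemoglobin levels at 4 months above" the anaemia threshold, and that they should therefore qualify as donors. The thresholds there are 13 g/dL for men and 11.5 g/dL for women, and the share above them is put at 60.4% or more. The same paragraph notes that the copper sulphate cut-off for women is 12 g/dL, and that "under these assumptions 50% of women would pass the copper sulphate test".

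The primary outcome "of the trial is haemoglobin level (g/dl) after 4 months" (SAP 7.2.1). "A 1-sided t-test for the regression coefficient associated with group membership will be conducted with a significance level of 0.025", in a linear model that also contains screening haemoglobin, sex and age. "The non-inferiority margin is fixed at a value of 1.0 g/dL" (SAP 2.4). The iron arm takes everyone with iron deficiency (ID), iron deficiency anaemia (IDA) or low haemoglobin.

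The efficacy outcomes in SAP 7.2.2 are change in haemoglobin, ferritin at 4 months, diagnosis of ID or IDA at 4 months, attempted donation within 6 months, and "Successful donation within 6 months (Yes or No"). A full blood count is scheduled at screening and at 2, 4 and 6 months.

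**The concern.** The margin is defended by a statement about individuals (most will pass), but the test concerns an adjusted difference in means. If the first does not follow from the second, a positive primary result could be reported as showing that most low-haemoglobin donors become eligible when they have not.

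The listed outcomes do not fill the gap. Every category in Protocol Table 4 requires ferritin below 15 µg/L, so a participant who is still anaemic with corrected ferritin does not count as having ID or IDA, while one with ID but normal haemoglobin does. The SAP gives iron for low haemoglobin alone, so the first kind of participant is to be expected. The donation outcomes depend on the participant choosing to return, and they cover 6 months. The proportion who regain eligibility at 4 months is a figure that planning of the UH3 phase would need.

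**Working it through.** **Inputs.** SD 1.89 g/dL, margin 1.0 g/dL, 131 per arm, one-sided alpha 0.025 (SAP 2.4). Thresholds 13 and 11.5 g/dL, copper sulphate cut-off for women 12 g/dL, half of donors anaemic (SAP 1.2).

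**1. The plan's figures reproduce.**
- Subgroup means are threshold ± 1.89 × √(2/π) = threshold ± 1.51. This gives 11.5 and 14.5 for men, 10.0 and 13.0 for women.
- At the margin the means are 13.5 and 12.0. The share above the anaemia threshold is Φ(0.5/1.89) = 60.4% for both sexes.
- Women at the 12 g/dL cut-off: Φ(0/1.89) = 50%.
- Table 3 (65, 80, 101, 131, 179) and 262/0.90, rounded up to 292, also reproduce.

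**2. Mixed iron arm.** The 60.4% needs the whole iron arm to have low haemoglobin. Let a fraction f have it, and assume that the others (ID without anaemia) average 14.5 g/dL. For men with an arm mean of 13.5, the low-haemoglobin mean is (13.5 − (1 − f) × 14.5)/f, and the share above 13 is Φ((mean − 13)/1.89):

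| f | Low-Hb mean (g/dL) | Share above 13 |
|---|---|---|
| 1 | 13.50 | 60.4% |
| 0.8 | 13.25 | 55.3% |
| 2/3 | 13.00 | 50.0% |
| 0.5 | 12.50 | 39.6% |

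**3. Adjustment for screening haemoglobin.** The margin argument compares unadjusted means (14.5 against 13.5). The test adjusts for the variable that largely defines the groups. Take the SAP's design case for men: population mean and threshold 13, SD 1.89 at both visits, groups split at 13, 131 per arm. Assume **no iron effect** and a screening-to-4-month correlation r, which the documents do not give.
- Expected unadjusted difference: −r × 2 × 1.51.
- Expected adjusted coefficient: 0, because the groups lie on one regression line.
- SE of the coefficient: 1.89 × √(1 − r²) × √(2/131)/√(1 − 2/π), where 2/π is the squared correlation of group with screening haemoglobin.
- Probability of declaring non-inferiority: about Φ(1/SE − 1.96).
- Share of low-haemoglobin men reaching 13: 1/2 − arcsin(r)/π.

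| r | Unadjusted difference | SE | Non-inferiority declared | Low-Hb men reaching 13 |
|---|---|---|---|---|
| 0.6 | −1.81 | 0.310 | 90% | 30% |
| 0.7 | −2.11 | 0.277 | 95% | 25% |
| 0.8 | −2.41 | 0.232 | 99% | 20% |

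Simulation of the fitted model agrees to within about 1 point (89% at r = 0.6). Applying the exclusion of haemoglobin below 10 g/dL gives roughly 87%, 94% and 99%, with 32%, 28% and 23% reaching 13. The illustration leaves out allocation by ferritin, age, and any drift in the population mean.

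**4. Precision of a direct estimate.** The half-width is 1.96 × √(p(1 − p)/n). At p = 0.604 it is 8.4 points for n = 131, 9.6 for 100 and 12.4 for 60. At p = 0.5 and n = 60 it is 12.7. The documents do not give the number of low-haemoglobin participants in the iron arm, so n is assumed.

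**The case against.** The strongest reply is that the SAP paragraph justifies a margin under stated assumptions and plans no formal conclusion that a majority qualifies. The stated hypothesis is recovery to near the level of those not given iron. Haemoglobin is measured in everyone at 4 months, so the proportion can be computed whenever it is wanted. All of that is correct. It limits the gap to a missing endpoint, but it does not make the inference from means valid.

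A second reply is that an observed difference of −1.0 would fail. Unadjusted, the observed difference must exceed −1 + 1.96 × 1.89 × √(2/131) = −0.54. On the plan's assumptions that corresponds to about 69% of men above 13.0 and 60% of women above 12.0. This holds only for an unadjusted comparison in an arm made up wholly of low-haemoglobin participants, and the plan has neither.

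A third reply is that a single-arm proportion in people selected for low haemoglobin contains regression to the mean. That stands. The estimate should sit beside the controlled comparison, not replace it.

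A reader might also infer from the schedule that the week-24 "NBSG Pre-Donation Assessment" is the only test of eligibility, and that a fall in haemoglobin after iron stops would be read as failure of the 4-month intervention. The documents do not support either inference:
- The SAP sentence concerns the anaemia threshold, which the 4-month blood count can address.
- Return donation status is recorded at both interim visits and the final visit.
- Nothing treats week-24 results as the 4-month result, and the planned longitudinal models would show a later change.
- No source is given for the size of any fall.
- Whether iron has ended by week 24 is unsettled. The Protocol's Treatment paragraph allows 16 weeks or to the end of follow-up, while its safety section gives 4 months (16 weeks). Those passages must be reconciled.

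**Conclusion.** The concern holds in limited form. The step from the 1 g/dL margin to a majority passing is not secured by the primary analysis, and no listed efficacy outcome estimates that majority. In the SAP's design case for men, a treatment with no effect would pass the adjusted test about nine times in ten or more while roughly a quarter of low-haemoglobin men reach the threshold. That result rests on a normal distribution, a split on haemoglobin alone and an assumed correlation of 0.6 to 0.8. The mixed-arm result rests on an assumed mean of 14.5 g/dL for iron-deficient participants without anaemia. Neither predicts what this trial will find. They show only that a positive primary result need not mean that most would qualify. The missing piece is a pre-specified estimate, not a visit or a test.

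**What to change.** In SAP 7.2.2, add a secondary efficacy outcome: among iron-arm participants below the sex-specific anaemia threshold at screening (13.0 g/dL for men, 11.5 g/dL for women), the proportion above that threshold by full blood count at Interim Visit 2, by sex, with an exact 95% confidence interval. Alongside it, report the proportion at or above the copper sulphate values (13.0 and 12.0 g/dL), because the two cut-offs differ for women.

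State that any conclusion that most would qualify as donors rests on these estimates and not on the non-inferiority result. Add that a single-arm proportion in people selected for low haemoglobin includes regression to the mean and does not replace the controlled comparison.

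The cost is SAP wording only. The blood count is already scheduled, and SAP 1.1 allows updates until database lock. Separately, reconcile the two Protocol statements on the duration of iron.
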